9.7.1.6.2 SECONDARY EFFICACY ANALYSES

The MCI/Prodromal Cohort

An MMRM will be used to analyze the following secondary endpoint: (revised per Amendment 02)

- Change from baseline in total hippocampal atrophy at 12 and 18 months of treatment in MCI/Prodromal subjects as measured by vMRI

Comparisons between each treatment group and placebo will be performed.

The Mild to Moderate AD Cohort (revised per Amendment 01)

The MMRM will be used to analyze the change from baseline of derived ADCOMS at 18 months in mild to moderate AD. If there is no treatment group-by-population interaction in the overall study, the MMRM analysis will include all subjects (MCI/Prodromal or mild to moderate AD) in the overall study. Otherwise, the MMRM analysis will only include subjects in the Mild to Moderate AD cohort. The comparison between placebo and active doses will be performed within mild to moderate AD subjects regardless of subjects included in the MMRM analysis. Dunnett's method will be used to control for multiplicity due to multiple comparisons.

9.7.1.6.3 EXPLORATORY EFFICACY ANALYSES

(revised per Amendments 01, 02, and 04)

An MMRM will be used to analyze the following exploratory endpoints:

- Change from baseline in the derived ADCOMS at 12 months in MCI/Prodromal and mild to moderate AD subjects
- Change from baseline in total hippocampal atrophy at 12 and 18 months in mild to moderate AD subjects as measured by vMRI
- Change from baseline in CSF A β (1-x) and CSF A β (1-42) after at least 4 weeks and at 18 months in MCI/Prodromal and mild to moderate AD subjects. Data from early discontinuations will also be included. (revised per Amendment 04)
- Change from baseline in the clinical assessments: ADAS-cog, CDR, MMSE, ISLT, CBB, and FAQ at 12 weeks and at 6, 9, 12, 15, 18, 19, and 21 months in MCI/Prodromal and mild to moderate AD subjects
- Change from baseline in plasma and CSF amyloid and CSF BACE1 measurements after 4 weeks and 18 months of treatment, and during post-treatment follow-up in MCI/Prodromal and mild to moderate AD subjects
- Change from baseline in left and right hippocampal, whole brain, and total ventricular volume at 6, 12 and 18 months as measured by vMRI in MCI/Prodromal and mild to moderate AD subjects

A linear mixed-model will be used to analyze the following exploratory endpoints:

- Change from baseline in brain amyloid levels as measured by amyloid PET at 18 months in MCI/Prodromal and mild to moderate AD subjects
- Change from baseline in CSF biomarkers of neurodegeneration (eg, tau, p-tau) at 18 months of treatment in MCI/Prodromal and mild to moderate AD subjects

Data from early discontinuations will also be used as appropriate. Comparisons between each treatment group and placebo will be performed.

A linear mixed-model with repeated measures will be used to determine the relationship between the following endpoints:

- Change from baseline in the derived ADCOMS score and the change from baseline in biomarkers in CSF at 18 months in MCI/Prodromal and mild to moderate AD subjects
- Change from baseline in the derived ADCOMS score and change from baseline in imaging biomarkers (hippocampal, whole brain, and total ventricular volumes) at 12 and 18 months in MCI/Prodromal and mild to moderate AD subjects

ApoE status for heterozygous and homozygous E4 carriers will be included in the model to assess the effect of *ApoE* status in this relationship.

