8.3 Exploratory Objectives

(revised per Amendments 01,02, and 04)

The exploratory objectives are:

1. To explore the effect of E2609 compared with placebo on the derived ADCOMS following 12 months of treatment in MCI/Prodromal and mild to moderate AD subjects
2. To explore the effect of E2609 compared with placebo on total hippocampal atrophy at 12 and 18 months of treatment in mild to moderate AD subjects, as measured by vMRI
3. To explore the effects of E2609 compared with placebo on A β (1-x) and A β (1-42) in CSF after at least 4 weeks and at 18 months of treatment in MCI/Prodromal and mild to moderate AD subjects
4. To explore the effects of E2609 compared with placebo on clinical status at various time points during 18 months of treatment, and during post-treatment follow-up, in MCI/Prodromal and mild to moderate AD subjects, by assessment of:
 - a. The Alzheimer's Disease Assessment Scale – cognitive subscale (ADAS-cog)

-
- b. The Clinical Dementia Rating (CDR) scale
 - c. The Mini-Mental State Examination (MMSE)
 - d. The CogState Brief Battery (CBB)
 - e. The Functional Assessment Questionnaire (FAQ; (also known as the Functional Activities Questionnaire)
 - f. The International Shopping List Task (ISLT)
5. To explore the effects of E2609 compared with placebo on various biomarkers in MCI/Prodromal and mild to moderate AD subjects. Biomarkers to be explored include, but not limited to:
 - a. CSF biomarkers of neurodegeneration (eg, tau, phosphorylated-tau [p-tau]) after 18 months of treatment
 - b. Plasma and CSF amyloid, and CSF BACE1 measurements during 18 months of treatment and during post-treatment follow-up
 - c. vMRI measurements including left and right hippocampal volume, whole brain volume, and total ventricular volume at 6, 12, and 18 months of treatment and during post-treatment follow-up
 - d. Brain amyloid levels at 18 months as measured by amyloid positron emission tomography (PET)
 6. To characterize the population PK of E2609 in MCI/Prodromal and mild to moderate AD subjects, and to examine the effect of intrinsic and extrinsic factors (including N-acetyltransferase 2 [*NAT2*] phenotype) on the PK
 7. To explore the relationship between the treatment effects of E2609 on the ADCOMS and its effects on CSF amyloid, CSF BACE1, CSF tau, and vMRI in MCI/Prodromal and mild to moderate AD subjects

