Annualized rates of change of 2% to 3% have been reported for the AD brain compared with 1% in MCI and <1% in age-matched controls (Hua, et al., 2010, Leung, et al., 2010). However, subjects with MCI due to AD-dementia (CSF A β <192 pg/ml or positive amyloid imaging) show rates of atrophy comparable to those observed in subjects with AD-dementia (Hua, et al., 2009; Hua, et al., 2010; Leung, et al., 2010; Morra, et al., 2009), supporting the notion that such subjects are on similar trajectories as those with mild AD-dementia. Lower levels of CSF A β 42, amyloid positivity on PET imaging, and higher levels of CSF t-tau in addition to the presence of the *ApoE4* allele have all been associated with greater rates of brain atrophy (Fjell, et al., 2010a; Fjell, et al., 2010b) and will be entered as covariates in various analyses. Hippocampal atrophy has also been shown to predict clinical progression independently of amyloid levels in the brain (Jack, et al., 2010), and this measure will be entered as a covariate in the analysis of the clinical endpoints along with the aforementioned variables.

Brain volume (total ventricular volume, whole brain, temporal lobe) generally shows a modest correlation with performance on a number of cognitive scales (Hua, et al., 2009; Hua, et al., 2010; Freeborough, et al., 1997; Leung, et al., 2010). Using volumetric analysis performed at 6-month intervals, these relationships and the effects of E2609 treatment will be explored further. Recent advances in analysis software have made structural imaging more sensitive to detect small changes and able to reliably measure rates of atrophy at these intervals, particularly in the posterior parietal and the lateral temporal regions during the early stages of disease (Hua, et al., 2009; Hua, et al., 2010). Given these observations, a demonstration of significant slowing or stabilization in the rate of atrophy in response to treatment, compared with placebo, will offer further support for disease modification.

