9.7 Statistical Methods

All statistical analyses will be performed by the sponsor or designee. Statistical analyses will be performed using SAS software or other validated statistical software as required.

All statistical tests will be based on the 5% (2-sided) level of significance, except for the Bayesian methods on the primary endpoint.

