Statistical methods for the final conventional analyses will use a mixed-effects model with repeated measures (MMRM) on the change from baseline in the derived ADCOMS at 18 months. The model will include treatment groups, randomization stratification variables (the presence or absence of ongoing treatment with AChEIs or memantine or both, and *ApoE4* status), and baseline ADCOMS as covariates. Other covariates such as adjusted hippocampal volume will be studied. These analyses will be performed as sensitivity analyses on the FAS as well as the PP set and as such, no multiplicity adjustments will be made to account for the interim analyses. In case of early success, the conventional analyses will also be performed using the data collected before the interim analysis.

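### The model that links ADCOMS to the biomarkers tests subject-level association of change, whereas exploratory Objective 7 asks about treatment effects

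*Protocol*

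**What the plan says.** Protocol Section 8.3, Objective 7, reads in part "To explore the relationship between the treatment effects of E2609 on the ADCOMS and its effects on CSF amyloid", and goes on to name CSF BACE1, CSF tau and vMRI.

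The matching analysis is at the end of Section 9.7.1.6.3 and is repeated in the Synopsis: "A linear mixed-model with repeated measures will be used to determine the relationship between the following endpoints". Two pairs follow. The first is "Change from baseline in the derived ADCOMS score and the change from baseline in biomarkers in CSF at 18 months". The second is "Change from baseline in the derived ADCOMS score and change from baseline in imaging biomarkers"; these are the vMRI volumes, taken at months 12 and 18. The one covariate mentioned is ApoE, whose "status for heterozygous and homozygous E4 carriers will be included in the model to assess the effect of" ApoE on the relationship. The sentence promising comparisons with placebo closes the list before this one and does not belong to this model.

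Section 9.7 sets the test level: "All statistical tests will be based on the 5% (2-sided) level of significance", with the Bayesian primary analysis excepted.

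On natural history, Section 9.2.5.4 states that brain volume "generally shows a modest correlation with performance on a number of cognitive scales" and that hippocampal atrophy predicts clinical progression. Section 9.2.5.2 states that t-tau and p-tau rise as the disease progresses.

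**The concern.** A treatment effect is a difference between a dose arm and placebo. Objective 7 asks whether two such differences go together. The planned model asks whether subjects whose biomarker moved more also moved more on ADCOMS. Its null hypothesis is no correlation of change between subjects.

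The protocol's own rationale leads one to expect that null to be false without any drug, at least for atrophy and tau, because faster progressors worsen on both measures. A significant slope could then be read as biomarker support for a drug effect on ADCOMS, although an all-placebo trial could produce it too. A genuine dose-level link could not be told apart from natural history.

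**Working it through.** The protocol gives no sample size, power or error rate for this analysis, so there is no figure to reproduce. The check is the chance of a two-sided p < 0.05 for the slope when E2609 affects neither measure.

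**Inputs from the protocol**
- Two-sided 5% level (Section 9.7).
- Up to 500 MCI/Prodromal and 200 mild to moderate AD subjects (Sections 9.7.2.1 and 9.7.2.2).
- 20% attrition at 18 months, stated for vMRI (Section 9.7.2.1), giving 500 × 0.8 = 400, 200 × 0.8 = 160 and 700 × 0.8 = 560.

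**Assumptions**
- Natural within-subject correlation r of the two changes: 0.1 to 0.3. The protocol says only that the brain volume correlation is modest.
- CSF subset: 10% to 25% of 560, so 56 to 140. CSF consent is voluntary (Section 5.3) and no number is given.
- The 20% attrition applies to both cohorts. One time point, month 18.

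**Formula (Fisher z)**

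m = atanh(r) × √(n − 3); P = 1 − Φ(1.96 − m) + Φ(−1.96 − m)

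For n = 400:
- r = 0.1: m = 0.1003 × 19.92 = 2.00, so P ≈ Φ(0.04) = 0.52.
- r = 0.2: m = 0.2027 × 19.92 = 4.04, so P ≈ Φ(2.08) = 0.98.

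| Setting | n | r = 0.1 | r = 0.15 | r = 0.2 | r = 0.3 |
|---|---|---|---|---|---|
| Imaging, MCI/Prodromal | 400 | 52% | 85% | 98% | about 100% |
| Imaging, mild to moderate AD | 160 | 24% | 47% | 72% | 97% |
| Imaging, both cohorts, if pooled | 560 | 66% | 95% | 99.8% | about 100% |
| CSF, 25% of 560 | 140 | 22% | 42% | 66% | 95% |
| CSF, 10% of 560 | 56 | 11% | 20% | 31% | 62% |

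At r = 0 the rate is 5%.

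**Does a dose covariate help?** A simulation with four equal arms, a three-level ApoE covariate and month-18 data only fitted the slope with and without dose indicators (3,000 trials per cell, inert drug):

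| n | r | slope significant, no dose term | slope significant, dose term added | omnibus arm test on ADCOMS |
|---|---|---|---|---|
| 400 | 0.1 | 51% | 51% | 5% |
| 400 | 0.2 | 98% | 98% | 4% |
| 140 | 0.2 | 66% | 65% | 4% |

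The rates barely change. Dose indicators remove the between-arm part of the association, which is the part that carries the randomised contrasts, and leave the within-arm part. Natural progression lives in the within-arm part. The arm test on ADCOMS is shown only to confirm that the drug is inert in these trials; it is not itself an analysis of Objective 7.

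**A drug that moves the biomarker but not ADCOMS.** With biomarker shifts of 0.25, 0.5 and 0.75 SD across the doses and no ADCOMS effect (1,500 trials, n = 400, r = 0.2), the slope is significant in 98% of trials and the arm test on ADCOMS in about 5%. A significant slope therefore does not show that the two treatment effects go together.

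**The case against.** The strongest reply has four parts.

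- **Detail belongs in the SAP.** Section 9.7.1 defers further detail to the SAP, and Section 9.7.1.7.2 allows a separate plan for biomarkers. A reader might infer from the ApoE sentence that dose is left out, particularly since the ADCOMS MMRM in Section 9.7.1.6.1 says "The model will include treatment groups, randomization stratification variables". The text does not support that. It names ApoE for a purpose and gives no closed covariate list, and it does not say which variable is the outcome. This part stands, but it does not rescue the analysis. The mismatch lies in what the protocol does fix, individual changes in place of randomised contrasts, and a dose covariate leaves the rates unchanged.
- **Pooling is not stated.** A reader might infer that the two cohorts go into one model. The phrase naming both cohorts is used for nearly every exploratory endpoint, and Section 9.2.3 says the cohorts are analysed independently for decision making. This stands, so the conclusion rests on the MCI/Prodromal cohort alone.
- **The natural correlation is not quantified.** Section 9.2.5.4 speaks of brain volume and cognitive performance, not of change against ADCOMS change. For CSF amyloid and BACE1 no natural correlation of change with ADCOMS change is given. This stands and limits how firmly the rates can be stated.
- **The randomised contrasts are planned elsewhere.** Atrophy is compared with placebo, the ADCOMS MMRM contains treatment, and Section 9.7.1.7.2 relates biomarkers to dose and exposure. This is true, but nothing described sets the two treatment effects against each other, which is what Objective 7 asks.

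**Conclusion.** The point holds as a mismatch between objective and analysis. As described, the model tests subject-level association and cannot by itself support a statement about treatment effects. With an inert drug it can be significant in about 52% of trials at r = 0.1 and 98% at r = 0.2 for imaging in the MCI/Prodromal cohort (n = 400). The case is clearest for vMRI and plausible for tau. For CSF the rate runs from about 11% to 95% over the assumed 56 to 140 subjects and r of 0.1 to 0.3; for CSF amyloid and BACE1 these rates are illustrative only. All figures rest on the assumed correlations, the assumed CSF share and a single time point.

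A reader might also infer that this slope would steer Phase 3. The documents do not support that: no decision rule uses it, and Section 9.2.5.4 looks for disease-modification support in slowing of atrophy compared with placebo. The risk is one of misreading an exploratory result.

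**What to change.** In Section 9.7.1.6.3 and the Synopsis:

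1. For Objective 7, within each cohort, plot and estimate the placebo-adjusted ADCOMS difference per dose against the placebo-adjusted biomarker difference per dose. Take intervals from resampling subjects within arm.
2. Keep the planned slope, but label it a subject-level (natural-history) association and state that it will not be used for claims about treatment effects.

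Do not rely on adding dose to the slope model, which leaves the problem in place. Do not enter dose indicators together with dose-group biomarker means either: within a cohort the two are collinear.

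This changes the wording of one exploratory analysis and needs no new data. The cost is precision: the dose-level estimate rests on three contrasts with placebo (two for mild to moderate AD subjects randomised in Stage B), and for CSF on a voluntary subset.

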9.7.1.7 Pharmacokinetic, Pharmacodynamic, Pharmacogenomic, and Other Biomarker Analyses

9.7.1.7.1 PHARMACOKINETIC ANALYSES

The PK Analysis Set will be used for E2609 concentration listings and for summaries of E2609 concentrations in plasma and CSF by dose and day. E2609 metabolite PK data may also be listed and summarized. (revised per Amendment 04)

A population PK approach will be used to characterize the plasma PK of E2609. For this approach, plasma PK data from this study will be pooled with relevant data from Phase 1 studies. As appropriate, the effect of covariates on the PK of E2609 will be evaluated. The PK model will be parameterized for oral clearance (CL/F) and apparent volume of distribution (V_z/F) for E2609. Derived exposure parameters such as steady state area under the concentration time curve (AUC) and average concentration (C_{avg}) of E2609 and other derived parameters will be calculated from the model using the individual estimates parameterized for oral clearance and dosing history. (revised per Amendment 04)

9.7.1.7.2 PHARMACODYNAMIC, PHARMACOGENOMIC, AND OTHER BIOMARKER ANALYSES

Pharmacodynamic, PGx, and other biomarker analyses may be performed and reported separately. Details of these analyses may be described in a separate statistical analysis plan. Please also refer to [Appendix 3](#).

Pharmacodynamic Analyses

The PD Analysis Set will be used for the summaries and analyses of PD biomarkers (CSF and plasma biomarkers, MRI endpoints). The percentage change from baseline in CSF A β (1-x), A β (1-42), A β (1-40), t-tau, p-tau, and BACE1 variables (eg, activity and protein levels) after at least 4 weeks and at 18 months will be analyzed and presented graphically. Baseline levels and changes in t-tau and p-tau will be correlated with changes in CSF A β (1-42), imaging markers, and *ApoE4* status. (revised per Amendment 04)

Summary statistics for CSF biomarkers will be assessed for evidence of a dose relationship.

Pharmacokinetic and Pharmacodynamic Analyses

The PK/PD relationship between CSF biomarker levels, amyloid load on PET, vMRI, and E2609 dose, plasma, and CSF exposure will be initially explored graphically and any emergent relationship will be explored through population PK/PD modeling. The PK/PD relationship between plasma PK parameters with other biomarkers may also be explored using similar methods. (revised per Amendment 04)

The relationship between plasma and CSF exposure to E2609 and the clinical efficacy scales (eg, MMSE, CDR) will be explored graphically. Additionally, the relationship between plasma exposures of E2609 and select lymphocyte parameters will be explored graphically, and any emergent relationship will be explored using population-based modeling methods. (revised per Amendment 04)

Exposure-safety analyses may also be conducted.

Pharmacogenomic Analyses

Blood samples will be used to determine the *ApoE* genotype and the *NAT2* phenotype of subjects enrolled in this study. The genomic DNA samples may also be stored and used as described in [Section 9.7.1.7.2](#). Details of PGx testing may be provided and reported separately.

9.7.1.8 Safety Analyses

Evaluations of safety will be performed on the Safety Analysis Set. The incidence of AEs (including changes from baseline in physical and neurological examinations, and dermatological assessments), out-of-normal-range laboratory safety test variables, abnormal ECG findings, out-of-range vital signs, suicidality (C-SSRS), and results of the sleep questionnaire, along with the change from baseline in laboratory safety test variables, ECGs, safety MRI, and vital sign measurements will be summarized by treatment group using descriptive statistics.

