9.7.1.4 Demographic and Other Baseline Characteristics

Demographic and other baseline characteristics for the Safety Analysis Set and FAS will be summarized for each treatment group using descriptive statistics. Continuous demographic and baseline variables include age, MMSE and FAQ; categorical variables include sex, age group (≤ 65 years, age > 65 years), race, ethnicity, *ApoE4* status (positive or negative), prior treatment with AChEIs or memantine (no or yes), and clinical population (MCI/Prodromal AD or mild to moderate AD). (revised per Amendment 01)

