9.7.1.8.2 ADVERSE EVENTS

The AE verbatim descriptions (investigator terms from the eCRF) will be classified into standardized medical terminology using the Medical Dictionary for Regulatory Activities (MedDRA). Adverse events will be coded to the MedDRA (Version 17.0 or higher) lower level term closest to the verbatim term. The linked MedDRA preferred term and primary system organ class (SOC) are also captured in the database.

A TEAE is defined as an AE that emerges during treatment, having been absent at pretreatment (Baseline) or

- Reemerges during treatment, having been present at pretreatment (Baseline) but stopped before treatment, or
- Worsens in severity during treatment relative to the pretreatment state, when the AE is continuous.

Only those AEs that are treatment-emergent will be included in summary tables. All AEs, treatment-emergent or otherwise, will be presented in subject data listings.

The TEAEs will be summarized by treatment group on the Safety Analysis Set. The incidence of TEAEs will be reported as the number (percentage) of subjects with TEAEs by SOC and preferred term. A subject will be counted only once within an SOC and preferred term, even if the subject experienced more than 1 TEAE within a specific SOC and preferred term. The number (percentage) of subjects with TEAEs will also be summarized by maximum severity (mild, moderate, or severe). The number (percentage) of subjects with TEAEs will also be summarized by relationship to study drug (Yes [related] and No [not related]).

The number (percentage) of subjects with treatment-related TEAEs will be summarized by SOC and preferred term. Treatment-related TEAEs include those events considered by the investigator to be related to study drug. The number (percentage) of subjects with treatment-related TEAEs will also be summarized by maximum severity (mild, moderate, or severe).

Adverse events will be summarized by the following subgroups: *ApoE4* status (positive or negative), prior treatment with AChEIs or memantine (no or yes), and clinical population (MCI/Prodromal or mild to moderate AD). (revised per Amendment 01)

The number (percentage) of subjects with TEAEs leading to death will be summarized by MedDRA SOC and preferred term for each treatment group. A subject data listing of all AEs leading to death will be provided.

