The number (percentage) of subjects with treatment-emergent SAEs will be summarized by MedDRA SOC and preferred term for each treatment group. A subject data listing of all SAEs will be provided.

The number (percentage) of subjects with TEAEs leading to discontinuation from study drug will be summarized by MedDRA SOC and preferred term for each treatment group. A subject data listing of all AEs leading to discontinuation from study drug will be provided.

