9.7.1.8.3 LABORATORY VALUES

Laboratory results will be summarized using International System of Units, as appropriate. For all quantitative parameters listed in [Section 9.5.1.5.3](#), the actual value and the change from baseline to each postbaseline visit and to the end of treatment (defined as the last on-treatment value) will be summarized by visit and treatment group using descriptive statistics. Qualitative parameters listed in [Section 9.5.1.5.3](#) will be summarized using frequencies (number and percentage of subjects), and changes from baseline to each postbaseline visit and to end of treatment will be reported using shift tables. Percentages will be based on the number of subjects with both nonmissing baseline and relevant postbaseline results.

Laboratory test results will be assigned a low/normal/high (LNH) classification according to whether the value was below (L), within (N), or above (H) the laboratory parameter's reference range. Within-treatment comparisons for each laboratory parameter will be based on 3-by-3 tables (shift tables) that compare the baseline LNH classification to the LNH classification at each postbaseline visit and at the end of treatment. Similar shift tables will also compare the baseline LNH classification to the LNH classification for the highest and lowest value during the treatment period.

[Appendix 1](#) (Sponsor's Grading for Laboratory Values) presents the criteria that will be used to identify subjects with treatment-emergent markedly abnormal laboratory values (TEMAVs). Except for phosphate, a TEMAV is defined as a postbaseline value with an increase from baseline to a Grade of 2 or higher. For phosphate, a TEMAV was defined as a postbaseline value with an increase from baseline to a Grade of 3 or higher. When displaying the incidence of TEMAVs, each subject may be counted once in the laboratory parameter high and in the laboratory parameter low categories, as applicable.

Lymphocyte subsets measured (including but not limited to CD4 [T helper cells], CD8 [cytotoxic T cells], CD19 [B cells], CD16/CD56 [natural killer cells] and CD14 [macrophages] and regulatory T cells) will be summarized in the same manner as other

laboratory parameters. Mean lymphocyte subsets and the mean change from baseline in lymphocyte subsets will also be displayed graphically over time by dose.

Serum IgG, IgM, and IgA will be measured and summarized in the same manner as other laboratory parameters.

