9.7.1.8.4 VITAL SIGNS

Descriptive statistics for vital signs parameters (ie, systolic and diastolic BP, pulse, respiratory rate, temperature, weight), and changes from baseline will be presented by visit and treatment group.

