9.7.1.8.5 ELECTROCARDIOGRAMS

Descriptive statistics for ECG parameters and changes from baseline will be presented by visit and treatment group. Shift tables will present changes from baseline in ECG interpretation (categorized as normal; abnormal, not clinically significant; and abnormal, clinically significant) to the end of treatment.

In addition, the number (percentage) of subjects with at least 1 postbaseline abnormal ECG result in QTcF during the treatment period will be summarized. Clinically abnormal ECG results in QTcF will be categorized as follows:

Absolute QTc interval prolongation:

- QTc interval >450 msec
- QTc interval >480 msec
- QTc interval >500 msec

Change from baseline in QTc interval:

- QTc interval increases from baseline >30 msec
- QTc interval increases from baseline >60 msec

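### Non-adverse-event safety outputs are set by treatment group or dose across both cohorts, so the pooled 5 mg v placebo display can be confounded by cohort

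*Protocol*

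**What the plan says.** Section 9.7.1.2 defines a single Safety Analysis Set with no cohort restriction, and Section 9.7.1.8 uses it for all safety evaluations. The display factor is then fixed output by output:

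- Overall (9.7.1.8, whose list also covers C-SSRS and laboratory variables): "ECGs, safety MRI, and vital sign measurements will be summarized by treatment group using descriptive statistics".
- Laboratory values (9.7.1.8.3): by visit and treatment group, with immunoglobulins treated like the other laboratory parameters. For lymphocytes, "Mean lymphocyte subsets and the mean change from baseline in lymphocyte subsets will also be displayed graphically over time by dose".
- Vital signs (9.7.1.8.4): descriptive statistics "and changes from baseline will be presented by visit and treatment group".
- ECG (9.7.1.8.5): "Descriptive statistics for ECG parameters and changes from baseline will be presented by visit and treatment group".

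The one safety output with a stated cohort split is adverse events. Section 9.7.1.8.2 lists three subgroups, the last being "and clinical population (MCI/Prodromal or mild to moderate AD" (closing bracket omitted).

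On allocation, Sections 9.4.4 and 9.7.4 randomise AD subjects 1:1:1:1 to placebo, 5, 15 and 50 mg in Stage A. In Stage B they go 1:1:1 to placebo, 15 and 50 mg, with no 5 mg arm. Section 9.3 caps the AD cohort at about 200 including Stage A and puts no quota on either cohort in Stage A. MCI/Prodromal allocation becomes response-adaptive after the first 100 subjects. Section 9.1 gives each cohort its own placebo group in Stage B.

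**The concern.** Cohort is tied to dose by design. Most AD subjects enter in Stage B, where 5 mg is not available to them, yet their placebo subjects would fall into the same placebo column that 5 mg is read against. If the cohorts differ in laboratory course, ECG, vital signs or suicidality, a by-dose table or plot can show a 5 mg difference that is only cohort mix, or hide a real one.

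This matters because safety, with immunological and haematological parameters named, is a primary objective (Section 8.1), and Section 7 says the trial will guide the choice of Phase 3 doses. Section 9.2.3 itself argues for separate cohort analysis to keep AD data from confounding the MCI/Prodromal results. That argument appears in the design rationale and does not expressly govern safety, but the logic carries over.

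**Working it through.** **Does treatment group mean pooled?** The protocol does not say so outright. Three places point that way.

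- Section 9.7.1.4: "Demographic and other baseline characteristics for the Safety Analysis Set and FAS will be summarized for each treatment group using descriptive statistics". Among the variables listed is "clinical population (MCI/Prodromal AD or mild to moderate AD" (closing bracket omitted). Summarising cohort within a treatment group makes sense only if the group contains both cohorts.
- Section 9.7.1.6.2 refers to an interaction of treatment group with population in the overall study, so treatment group is used there as a label that crosses cohorts.
- The clinical-population subgroup for adverse events in 9.7.1.8.2 would be redundant if every table were already cohort-specific.

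**Cohort mix by arm.** The protocol states no figure to reproduce, so the mix follows from the ratios. Let A be the number of AD subjects in Stage A. Stage A is 60 ±20% with no cohort quota, so A runs from 0 to 72 (60 × 1.2, all AD). With 200 AD subjects:

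- AD on 5 mg = A/4
- AD on placebo, 15 mg and 50 mg = A/4 + (200 − A)/3 each
- AD share = AD/(AD + MCI)

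Taking 500 MCI/Prodromal subjects split equally (125 per arm, illustrative):

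| A | AD share, 5 mg | AD share, placebo (same for 15 and 50 mg) | 5 mg minus placebo |
|---|---|---|---|
| 0 | 0/125 = 0% | 66.7/191.7 = 34.8% | −0.348 |
| 30 | 7.5/132.5 = 5.7% | 64.2/189.2 = 33.9% | −0.283 |
| 72 | 18/143 = 12.6% | 60.7/185.7 = 32.7% | −0.201 |

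**Placebo subjects who could not have received 5 mg.** These are the Stage B AD placebo subjects, (200 − A)/3. At A = 0 they are 66.7/191.7 = 35% of the pooled placebo column; at A = 72 they are 42.7/185.7 = 23%.

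**Effect on a pooled display.** With no drug effect, the spurious difference is (AD share on dose − AD share on placebo) × D, where D is the AD minus MCI/Prodromal gap on that measure. Under equal allocation the multiplier for 5 mg is −0.20 to −0.35, and for 15 and 50 mg it is 0. The protocol gives no D. Purely as an illustration, assumed incidences of 10% (MCI/Prodromal) and 20% (AD) would give −2.0 to −3.5 percentage points.

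**Adaptive allocation.** The final MCI/Prodromal split is unknown. Under an assumed 170/60/60/210 (placebo/5/15/50 mg) with A = 0, the AD shares are 28.2%, 0%, 52.6% and 24.1%. The multipliers against placebo are −0.28, +0.24 and −0.04. With A = 72 the shares are 26.3%, 23.1%, 50.3% and 22.4%, and the 5 mg multiplier shrinks to −0.03. So other doses can be shifted, and for some allocations the 5 mg imbalance nearly vanishes.

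**The case against.** The strongest reply is that pooling is inferred. Section 9.1 also uses treatment groups within a cohort, the FAS is likewise a single set yet is analysed by cohort, and Section 9.7.1 leaves further detail to the statistical analysis plan, which could add cohort tables. This stands in part: nothing forbids cohort tables. But the protocol names the cohort split for one safety output and fixes a different display factor for the rest, so the pooled reading is the better one.

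It is also fair that no 5 mg v placebo test is prescribed and that the laboratory shift tables are within-treatment. A cohort difference in baseline level alone would not distort change-from-baseline columns. It would still show in the actual values, which are tabulated as well, and in the plotted lymphocyte means.

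For lymphocytes the gap may be small. Appendix 5 attributes low counts to age rather than disease, although it does not compare MCI with AD. The Stage A safety review is protected by 1:1:1:1 allocation in both cohorts, and the lymphocyte stopping rules use individual counts.

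A reader might infer that serious adverse events, deaths and discontinuations also lack a cohort split, since for instance "The number (percentage) of subjects with treatment-emergent SAEs will be summarized by MedDRA SOC and preferred term for each treatment group". The documents do not support that. These are adverse events, and on its plain reading the subgroup sentence in 9.7.1.8.2 covers them. Cognitive safety is outside the point too, because 9.7.1.8.6 refers to the cohort-based efficacy section.

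**Conclusion.** The point holds as a cheap improvement. Following the stated display rule puts 0 to 13% AD subjects on 5 mg beside 33 to 35% on placebo, assuming 200 AD subjects and 125 MCI/Prodromal subjects per arm. That contrast is not between randomised groups. It applies to laboratory, lymphocyte, immunoglobulin, ECG, vital-sign, safety MRI and C-SSRS outputs.

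A reader might go further and conclude that the 5 mg safety results will be biased by a definite amount. The documents do not support that. The cohort gap is not given, the adaptive splits above are assumed, and if the cohorts have the same safety course there is no bias. The outputs are descriptive, so no error rate changes.

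**What to change.** In Section 9.7.1.8, extend the clinical-population split already used for adverse events to laboratory values, lymphocyte-subset tables and plots, immunoglobulins, ECG, vital signs, safety MRI and C-SSRS. Show each by treatment group within cohort, against that cohort's own placebo group. State that any pooled 5 mg v placebo comparison rests on cohort-stratified results. The adverse event, serious adverse event, death and discontinuation tables need nothing beyond the existing subgroup sentence.

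The cost is wording and extra tables from data already collected. The AD 5 mg cells will be small, at most about 18 subjects (72/4).
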